10 PRIMARY ANALYSIS

10.1 Primary endpoint

The primary endpoint for the study is the incidence of reduced leaflet motion at a minimum of 30 days after the date of hospital discharge or ACT/DAPT discontinuation recorded on "Visit" e-CRF (expected within 1 to 6 months post-implant, preferably 3 months), as assessed by an independent Core Lab.

The valve leaflets will be assessed using 4D volume-rendered CT imaging or TEE for subjects unable to undergo CT scan (e.g. inappropriate renal function). Leaflet motion in all leaflets will be defined as normal, mildly reduced (<50% reduction in leaflet opening), moderately reduced (50-70% reduction in leaflet motion), severely reduced (>70% reduction in leaflet motion) and immobile (no or negligible leaflet motion).

10.2 TESTING STRATEGY AND MULTIPLICITY ADJUSTMENT

The primary statistical analysis will be focused on estimation rather than formal hypothesis testing confirmatory in nature, that is, two-side 90% CI will be provided instead of p-value. No adjustment for multiplicity will be made.

10.3 PRIMARY ENDPOINT DERIVATION

Reduced leaflet motion will be evaluated by means of the following parameters judged by Core Lab through the CT/TEE images:

Study: APR002 BELIEVE

- NL Orientation Left Motion
- NL Orientation Right motion
- NL Orientation Non Motion
- Rotated Left Non Motion
- Rotated Right Non Motion
- · Rotated Right Left Motion

Parameters will be judged by Core Lab as normal, mildly reduced (<50% reduction), moderately reduced (50 to 70% reduction), severely reduced (>70% reduction), or immobile (lack of motion in at least one valve leaflet).

No Reduction (success) of leaflet motion will be assigned if all of the above parameters will be recorded as normal or mildly reduced.

Reduction (failure) of leaflet motion will be assigned if at least one of the above parameters will be recorded as moderately reduced, severely reduced, or immobile.

Primary analysis will be based on results of the first CT scan as specified in the Table 2, using all subject in the SAF and done by overall.

Table 2: Use of CT scan results to define incidence in the primary analysis

Scenario #	Reduced leaflet motion at first CT scan	Primary Analysis
1	No	Not Reduction
2	Yes	Reduction

10.4 PRIMARY ANALYSIS

Incidence of reduced leaflet motion will be estimate as the proportion (\hat{p}) of subjects with reduced leaflet motion divided by the size of the population at risk in the SAF.

The 2-sided 90% CI will be calculated by means of Exact confidence limits based on the Binomial distribution.

10.5 SENSITIVITY ANALYSES

The analysis of the primary endpoints, which will provide incidence of reduced leaflet motion and its 90% CI, will be assessed in sensitivity analyses using different assumptions and populations (in each case, the same estimate and 90% CI calculation as specified in previous Section 10.4 will be applied):

COPYRIGHT LIVANOVA. ALL RIGHTS RESERVED. MAY NOT BE REPRODUCED WITHOUT PERMISSION. ALL HARD COPIES SHOULD BE CHECKED AGAINST THE CURRENT ELECTRONIC VERSION WITHIN MASTERCONTROL PRIOR TO USE AND DESTROYED PROMPTLY THEREAFTER. ALL HARD COPIES ARE CONSIDERED UNCONTROLLED DOCUMENTS.

LN-GLB-CLN-TEM-0033 rev1 Page 17 of 42

• Sensitivity Analysis 1: using the rationale to define the presence/absence of reduced leaflet motion as described in Table 3.

Study: APR002 BELIEVE

Table 3: Use of CT scan results to define incidence in the primary sensitivity analysis

Scenario #	Reduced leaflet motion at first CT scan	Reduced leaflet motion at second CT scan	Sensitivity Analysis 1
1	No	No	No Reduction
2	No	Yes	Reduction
3	Yes	No	No Reduction
4	Yes	Yes	Reduction

If the first CT scan showed no signs of reduced leaflet motion (scenario 1 and 2), a repeat exam is not mandated and will only be done if it becomes clinically indicated.

If no second CT scan will be performed, reduction/not reduction will be assigned as in Table 2.

- Sensitivity Analysis 2: using the PP population by excluding subject with major primary endpoint-related protocol deviations as described in Section 6.4.
- Sensitivity Analysis 3: Multiple Imputation (MI) analysis to adjust the primary analysis for the uncertainty introduced by the missing observations at first CT scan visit.

The objective of the MI (sensitivity analysis 3) is to impute reduction or no reduction for all subjects with missing values at first CT scan visit, and to perform this multiple time, so that the uncertainty or the imputation can be correctly accounted for in the analysis. Subject with missing data at first CT scan visit will have their missing value imputed according to *Missing At Random* assumptions and taking into consideration specific baseline characteristics.

The following steps will be carried out for the MI of missing data at first CT scan visit for the SAF set:

• The monotone missing data will be imputed using sequential regression multiple imputation, where a logistic regression model is estimated for imputation of the reduced leaflet motion (binary variable). The regression model will include as explanatory variables the age class [year], gender, ethnicity, presence of subject risk factor at baseline, NYHA at baseline, abnormality of ascending aorta or aortic root at implant, presence of aortic regurgitation measured by intraoperative TEE. These can be restricted to be age class [year], gender, ethnicity, presence of subject risk factor at baseline if convergence problem will occur.

Imputed data will consist of M=200 imputed datasets. This number may be reduced at Quality Control (QC) dry run if the amount of missing data is very low and incidence estimates are stable.

The random seed number for the sequential regression multiple imputation will be 2019.

Each of the M imputed datasets will be analyzed using the following analysis method:

COPYRIGHT LIVANOVA. ALL RIGHTS RESERVED. MAY NOT BE REPRODUCED WITHOUT PERMISSION. ALL HARD COPIES SHOULD BE CHECKED AGAINST THE CURRENT ELECTRONIC VERSION WITHIN MASTERCONTROL PRIOR TO USE AND DESTROYED PROMPTLY THEREAFTER. ALL HARD COPIES ARE CONSIDERED UNCONTROLLED DOCUMENTS.

LN-GLB-CLN-TEM-0033 rev1 Page 18 of 42

• Proportion of subjects with reduced leaflet motion will be analyzed based on observed and imputed data in the SAF. A logistic regression model will be performed using the observed/imputed binary data as the dependent variable and only the intercept as regression coefficient as $logit(\hat{p}) = log\left(\frac{\hat{p}}{1-\hat{p}}\right) = \beta_0 + \varepsilon$.

Study: APR002 BELIEVE

- Results from analysis of each imputed dataset will be combined using Little's and Rubin's imputation rules (Little and Rubin 1987) to produce a pooled predictive estimate of model intercept and its 90% confidence interval.
- Proportion \hat{p} , and its 90% CI, will be derived from the pooled estimates as $\hat{p}=rac{e^{\widehat{eta_0}}}{1+e^{\widehat{eta_0}}}$.

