recovery of motion was observed among TAVR and SAVR subjects who were treated with anticoagulation (11 of 21 subjects who underwent follow-up CT) using therapeutic doses of aspirin or warfarin. The median clinical follow up was 169-183 days and outcomes between subjects with reduced leaflet motion and those with normal motion were the same for death and MI. There was a higher incidence of stroke among the subjects in the pooled registries. Based on the echocardiography / CT findings of attenuated hypo-echoic opacities on the leaflets and the impact of anticoagulation, the hypothesized etiology of reduced leaflet motion is the development of leaflet thrombosis.

The incidence of reduced leaflet motion has not been previously evaluated in the Perceval valve in clinical studies. The objective of this study is to examine the incidence of reduced leaflet motion in the LivaNova commercially approved bioprosthetic aortic valve, Perceval, as assessed by four-dimensional, volume-rendered CT (4D CT), in both symptomatic* and asymptomatic subjects.

*Symptomatic subjects are those subjects with clinical symptoms, (such as, but not limited to shortness of breath, fatigue, or signs of thromboembolic events) and determined by the treating physician.

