2.3 SAMPLE SIZE CALCULATION

A sufficient number of subjects will be enrolled in this study to allow a minimum of 75 evaluable CT scans for the primary endpoint. Evaluable scans are those where a determination of normal or abnormal leaflet motion is possible. Considering an attrition rate of 15% of subjects, the sample size targeted for enrollment is approximately 88 subjects.

A sample size of 75 evaluable CT scans produces an Exact two-sided 90% CI with a width lower than 13% when the sample proportion is lower than 10% (evaluation calculated using PASS software, version 13).

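### SAP 10.5 Table 3 labels last-scan status as incidence, so Sensitivity Analysis 1 will nearly always equal or fall below the primary estimate and does not estimate incidence up to 1 year

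*SAP*

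**What the plan says.** The objective in SAP 2.1.1 and Protocol 3.1 is the overall incidence of reduced leaflet motion up to 1 year after implant. For the primary analysis, SAP 10.3 states: "Primary analysis will be based on results of the first CT scan as specified in the Table 2". A subject is a case if any leaflet parameter is moderately reduced, severely reduced or immobile. Normal and mildly reduced motion both count as no reduction.

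Sensitivity Analysis 1 (SAP 10.5) brings in the second scan, "using the rationale to define the presence/absence of reduced leaflet motion as described in Table 3". The title of Table 3 presents it as a definition of incidence. Its four scenarios are:

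| Scenario | First CT | Second CT | Table 3 result |
|---|---|---|---|
| 1 | No | No | No Reduction |
| 2 | No | Yes | Reduction |
| 3 | Yes | No | No Reduction |
| 4 | Yes | Yes | Reduction |

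Without a second scan, the first result stands.

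The schedules in Protocol 8.1 and SAP 2.2 assign the second CT to subjects with reduced motion on the first. For the others, SAP 10.5 says "a repeat exam is not mandated and will only be done if it becomes clinically indicated".

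SAP 11.3 analyses the second-scan secondary endpoint by taking its rule from Table 3, restricted to scenarios 3 and 4.

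**The concern.** Incidence up to 1 year counts subjects who had the finding at any time in that year. A subject whom the Core Lab scored positive at the first CT is such a case, and later recovery does not undo it. Scenario 3 removes that subject. Full normalisation is not needed: moving from moderate to mild is enough.

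The scan schedule makes the effect lopsided. Each first-CT positive is scheduled for the scan that can delete the case, while a first-CT negative can become a case only through an unscheduled scan. Treatment may also change between scans if the investigator is unblinded (Protocol 7.11). A case could then drop out because it was found and treated.

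The study is descriptive, so the proportion with its 90% CI is the main result. A second figure also called incidence, with the same type of interval but measuring something else, can be misread as a robustness check. Neither of the other two sensitivity analyses fills the gap. One uses the per-protocol set and the other imputes missing first scans. None of the three counts a subject who is positive on either scan.

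**Working it through.** **Inputs from the documents**
- n = 75 evaluable scans, with a planned exact 90% CI width below 13% when the sample proportion is below 10% (SAP 2.3).
- Interval method (SAP 10.4, applied to the sensitivity analyses by 10.5): "The 2-sided 90% CI will be calculated by means of Exact confidence limits based on the Binomial distribution".
- Enrollment (SAP 2.3): "Considering an attrition rate of 15% of subjects, the sample size targeted for enrollment is approximately 88 subjects".
- Recovery reported in the literature summary (Protocol 2.1): "11 of 21 subjects who underwent follow-up CT".

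**Assumptions.** The documents give no expected number of first-CT positives, resolutions or conversions for this study. I use 7 first-CT positives as the main example because it is the largest count below 10% of 75, and I vary the rest.

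**Step 1: reproduce the plan's figures.** The exact limits are lower = Beta quantile(0.05; x, n − x + 1) and upper = Beta quantile(0.95; x + 1, n − x). For x = 7 and n = 75 they are 4.5% and 16.8%, a width of 12.35 points. At exactly 10% (x = 7.5) the width is 12.69 points. Both are below 13. Enrollment is 75 / (1 − 0.15) = 88.2, against about 88 stated. The plan's figures hold.

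**Step 2: what Table 3 computes.**

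Sensitivity Analysis 1 count = first-CT positives − resolved (scenario 3) + converted (scenario 2).

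With 7 positives and no converters:

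| Resolved | Count | Estimate | Exact 90% CI |
|---|---|---|---|
| 0 | 7/75 | 9.3% | 4.5 to 16.8 |
| 2 | 5/75 | 6.7% | 2.7 to 13.5 |
| 3 | 4/75 | 5.3% | 1.8 to 11.8 |
| 4 | 3/75 | 4.0% | 1.1 to 10.0 |
| 7 | 0/75 | 0% | 0 to 3.9 |

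The cited recovery fraction is 11/21 = 52%. Applied to 7 positives it gives 7 × 11/21 = 3.67 resolved, leaving 3 or 4 cases. That is one point inside the table.

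Other starting counts behave the same way. With 5 positives and 2 resolved, 6.7% (2.7 to 13.5) becomes 4.0% (1.1 to 10.0). With 10 positives and 5 resolved, 13.3% (7.4 to 21.6) becomes 6.7% (2.7 to 13.5).

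**Step 3: what it would take to rise above the primary estimate.** Conversions must outnumber resolutions. With 7 positives and 4 resolved, more than 4 of the 68 first-CT negatives (4/68 = 5.9%) would need a clinically indicated repeat scan that proves positive. For 5 to 10 positives and 25% to 75% resolution, the break-even share of negatives runs from 1.25/70 = 1.8% to 7.5/65 = 11.5%.

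**Step 4: positive on either scan.** With 7 first-CT positives the estimate is 7/75 = 9.3% (4.5 to 16.8) with no converters and 8/75 = 10.7% (5.4 to 18.4) with one, however many resolve.

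**The case against.** **Limited reach.** The primary analysis does not use Table 3, the study is descriptive with no confirmatory test, the coding is pre-specified, and the absence of a mandated repeat scan is stated beneath the table. SAP 11.3 also gives shift tables between scans, so a careful reader could see the resolved cases. All of this stands and limits the weight of the point, but it does not make last-scan status an incidence.

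**The replacement is one-directional too.** A count of subjects positive on either scan cannot fall below the primary estimate, and with few repeat scans it may be close to it. That is true. It follows from the definition of incidence up to 1 year, which can only accumulate, and the replacement should be presented in that light. Last-scan status remains worth reporting under its own name.

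**The rescan trigger is not fully defined.** Protocol 6.2 lists mildly reduced motion as a grade, and Protocol 7.8 triggers the second CT on reduced motion without naming a grade. If mild reduction triggered it, some first-CT negatives under the SAP cut-off would be rescanned routinely and scenario 2 would be less rare. SAP 10.5, however, describes scenarios 1 and 2 as showing no sign of reduced motion, which favours the reading used here. The ambiguity remains.

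**The cited recovery rate does not transfer directly.** The 11/21 covers full or partial recovery in TAVR and SAVR subjects treated with anticoagulation. Here, investigators are asked not to alter such therapy in asymptomatic subjects, and partial recovery need not cross the moderate-to-mild boundary. This stands, so 11/21 is not a forecast.

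**Conclusion.** The point holds for Sensitivity Analysis 1. Table 3 reports status at the last available scan and calls it incidence. Given who is rescanned, it will nearly always equal or fall below the primary estimate, and it does not estimate incidence up to 1 year. In the example of 7/75 with no converters, the result lies anywhere from 9.3% down to 0%, depending on how many positives resolve. The starting count, the resolution numbers and the absence of converters are all assumptions.

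Three stronger readings might be inferred, and the documents do not support them:
- That the analysis can only lower the estimate. Scenario 2 allows a rise, and without repeat scans after a negative first CT the two estimates agree whenever no positive resolves.
- That the primary result is biased. It rests on the first CT alone and Table 3 does not touch it.
- That the estimate should be expected to fall by about half. That would treat 11/21 as this trial's recovery rate.

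The change should be made, but it concerns what one sensitivity analysis may be said to show, not the main result.

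**What to change.** 1. In SAP 10.5, define the incidence sensitivity analysis up to 1 year as positive on either scan, so that scenarios 2, 3 and 4 all count as Reduction. State that this estimate cannot fall below the primary one.
2. Keep the present Table 3 coding, but label it last-scan status (persistence or resolution).
3. Write that coding directly into SAP 11.3. Changing the scenario 3 cell alone would not be safe: 11.3 takes its rule from scenarios 3 and 4, and if both read Reduction, its proportion would be 100% by construction and secondary endpoint 2 would be lost.
4. Report the number of repeat scans by first-CT result, so that readers can see how much opportunity there was to add or remove cases.

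The cost is a small edit to 10.5 and 11.3 and one extra table. No new data are needed.

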11 SECONDARY EFFICACY ANALYSES

11.1 SECONDARY EFFICACY ENDPOINTS

The secondary efficacy endpoints for the study will be evaluated in the SAF and are:

- Incidence of reduced leaflet motion (thrombus) with subanalysis in symptomatic and asymptomatic subjects based on CT outcomes and ACT/DAPT modalities up to 1 year postimplant.
- Incidence of reduced leaflet motion on second 4D CT scan with contrast up to 1 year postimplant, in subjects in which reduced leaflet motion was previously detected.
- Incidence and relationship of reduced leaflet motion to the devices, procedure, or other causes up to 1 year post-implant.
- Freedom from valve safety events (all-cause mortality, valve re-intervention, myocardial
 infarction, structural valve deterioration, moderate or severe valve regurgitation, valve
 endocarditis, valve thrombosis, thromboembolic events, hemolysis and major bleeding) up
 to 1 year post-implant.
- NYHA classification at 1 year post-implant.

11.2 INCIDENCE OF REDUCED LEAFLET MOTION IN SYMPTOMATIC AND ASYMPTOMATIC SUBJECTS

Study: APR002 BELIEVE

Incidence of reduced leaflet motion up to 1 year post-implant will be evaluated separately in symptomatic and asymptomatic subject using the same method described for the evaluation of the primary analysis.

Symptomatic are those subjects with clinical symptoms, such as, but not limited to shortness of breath, fatigue, or signs of thromboembolic events, as assessed by the treating physician.

A subject will be identified as symptomatic as will be recorded in "Subject Clinical Assessment" e-CRF at the first CT scan visit. List of symptomatic subjects will be reviewed and validated by study team reviewers and confirmed by Steering Committee before data lock.

Within each symptomatic/asymptomatic subgroup, subjects will be categorized on the basis of medication used and discontinued at least 30 days before the first CT scan: any, anticoagulant only, dual antiplatelet medications only, anticoagulant and dual antiplatelet medications.

A forest plot will be used to graphically represent the estimate point of the proportion together with its 90% CI in each category (medication used within symptomatic/asymptomatic subjects); number of subject with reduced leaflet motion and number of total subject in each category will be also displayed.

In addition, all CT or TEE parameters, results and units received from Core Lab (see Sections $\underline{10.3}$ and $\underline{12}$), will be summarized descriptively, as appropriate in the correspondent visit, by overall and subgroup defined in Section 5.3. Details on reference range lower and upper limits will be listed by marking any abnormality with a flag. Leaflet categories (normal, mildly reduced, moderately reduced, severely reduced and immobile) will be also summarized including actual number and percentages.

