7.11. BLINDING OF CT IMAGING RESULTS

Blinding of CT imaging results, for the purpose of evaluation of reduced leaflet motion, has been implemented to minimize the PI's exposure to imaging information that would typically not be obtained through standard of care practices. This blinding is intended to

prevent influence of the subject's (medical) treatment based on the possible findings of the CT scan.

To limit access and visibility of the CT images they will be sent directly to the Core Lab, which will be responsible for the assessment. Core Lab findings will not be sent to the site or accessible to sites in the EDC system. If, through assessment of the CT scan, the Core Lab becomes aware of findings that would potentially jeopardize subject safety (i.e. thrombus), the PI will be notified. Any medical circumstance requiring the PI's access to the CT scan or imaging results will lead to unblinding of the PI, possible unblinding of the subject, and may result in an adjustment of the subject's treatment (including medication) based on the PIs discretion.

For asymptomatic subjects, PIs and subjects will be blinded from the CT imaging results and from the Core Lab findings. Investigators will be requested to not alter relevant antiplatelet or anticoagulation drug therapies for asymptomatic subjects. The need for and use of antiplatelet or anticoagulation drug therapy will be assessed at each follow-up visit.

Symptomatic subjects and the PI can be unblinded to CT imaging results based on any treatment deemed necessary by the PI or treating physician. In this case, the PI can request CT scan results from the Core Lab as they will not be automatically sent to the site. Symptomatic subjects are those with clinical symptoms, such as, but not limited to shortness of breath, fatigue, or signs of thromboembolic events, as assessed by the treating physician. Asymptomatic subjects with reduced leaflet mobility on their 1st CT scan, and who have an increase in valve gradients, may be unblinded. This determination will be made by the Core Lab and/or Coordinating Investigators, and revealed to the study site through the LivaNova Project Manager or designee.

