13. INDEPENDENT CLINICAL STUDY COMMITTEES

13.1. Steering Committee

A Steering Committee (SC) will be established to assist the Sponsor in designing and managing the study based upon scientific, medical and technical experience and expertise and providing advice on modifications or amendments to the protocol. The committee is comprised of at least two coordinating investigators; one with expertise in the diagnosis and management of cardiovascular disease and one with expertise in imaging. The SC will provide oversight of the study and recommend processes and procedures to ensure timely and accurate data collection and data quality. The SC will also support the site selection process and make recommendations about participating centers. A named member of the Sponsor's Clinical Affairs department will be part of the SC as a non-voting member, along with the coordinating investigators.

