4.3 OTHER STATISTICAL ANALYSES

Progress annual report may be prepared for eventual sending to the study team for internal evaluations of the study progress.

Specific statistical analysis may be provided to regulatory agencies upon request. In addition, internal evaluation could be requested during the study after assessing a reasonable number of subjects with results on the first CT scan at 1-6 months post-implant (i.e. every 50 subjects with the first CT-scan evaluation).

The Sponsor may also perform comparisons with previous studies in the same indication by means of meta-analytic approaches also using network meta-analyses, when required. More details will be presented in an ancillary SAP detailing this and any other exploratory analyses.

Additional statistical analyses may be run after the completion of the final analysis. In that case, an addendum of this SAP will be created describing the analyses to be performed.

5 Analysis convention

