18.13 DATA DERIVATIONS

Derived variable	Derivation algorithm based on e-CRF version 8 dated 18 th July 2017
Concomitant	"Implant Surgical Details" e-CRF:
Procedures	Group "Implanted with a concomitant procedure" if CPYN= "Yes"
	Group "Implanted without a concomitant procedure" if CPYN= "No"
Subject symptoms	"Subject Clinical Assessment" e-CRF at "at 1 Month After ACT Dx (1st CT-Scan)" or "Reduced Leaflet Visit (2nd CT-Scan)" Visits:
	Group "Asymptomatic" if SCSYMPYN = "No"
	Group "Symptomatic" if SCSYMPYN = "Yes"
ACT/DATP	"Subject Clinical Assessment" and e-CRF:
	 Group "Subject on ACT/DAPT at hospital discharged (or 30-days after implant)" if SCDISCYN= "Yes"
	Group "Subject off ACT/DAPT at hospital discharged (or 30-days after implant" if SCDISCYN= "No"
Core Lab evaluation	"Vist (at 1 Month After ACT Dx or at Reduced Leaflet)" e-CRF:
by	Group "CT scan" if IMGTYPE= "4D CT Acquisition"
	Group "TEE" if IMGTYPE = "Transesophageal Echo"
Pre-implant period	If Enrolled Date= DXSTDAT2 ("Implant Surgical Details" e-CRF) then
	Start date: ICFDAT ("Inclusion/Exclusion Criteria" e-CRF)
	End date: DXSTDAT2 -1
	If Enrolled Date= ICFDAT then
	Start date=End date= "None".

LN-GLB-CLN-TEM-0033 rev1 Page 39 of 42

Post-implant period	If DXPER= "Yes" ("Implant Surgical Details" e-CRF) Start date: DXSTDAT2, End date: if SCDISCYN= "No" ("Subject Clinical Assessment" e-CRF) then End date= VISDAT (at Hospital Discharge visit) + 30 if SCDISCYN= "Yes" ("Subject Clinical Assessment" e-CRF) then End date= VISDAT (et ACT Disceptionation visit) + 30
Post-ACT/DAPT period	 End date= VISDAT (at ACT Discontinuation visit) + 30 Start date: if SCDISCYN= "No" ("Subject Clinical Assessment" e-CRF) then Start date= VISDAT (at Hospital Discharge visit) + 31 if SCDISCYN= "Yes" ("Subject Clinical Assessment" e-CRF) then Start date= VISDAT (at ACT Discontinuation visit) + 31 End date: VISDAT (at Year 1 visit)
Implant procedure completer	 DXPERF= "Yes" ("Implant Surgical Details" e-CRF) and DSSTDAT ≥ ACTDIDAT ("Study Termination" e-CRF) + 31 o if DSSTDAT missing, last available VISDAT ≥ ACTDIDAT + 31
Study completer	DSDECOD= "Completed" ("Study Termination" e-CRF)
SCR population	ICFDAT not missing ("Inclusion/Exclusion Criteria" e-CRF)
Enrolled Date	Derived from maximum between Consent Date and Implant Date. "Inclusion/Exclusion Criteria" e-CRF and "Implant Surgical Details" e-CRF Max(ICFDAT; DXSTDAT2)

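### The pre-lock review of symptom status is not masked to CT results, so the symptomatic/asymptomatic split of incidence could be biased in either direction

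*SAP*

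**What the plan says.** **Symptom status.** SAP 11.2 starts from the site record: "A subject will be identified as symptomatic as will be recorded in 'Subject Clinical Assessment' e-CRF at the first CT scan visit". Symptoms are those judged present by the treating physician, and the examples given are explicitly not exhaustive. The same section then adds the review: "List of symptomatic subjects will be reviewed and validated by study team reviewers and confirmed by Steering Committee before data lock". It gives no criteria for the review and does not say what the reviewers may see.

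**Who reviews.** Study team reviewers are not defined. Protocol 13.1 says of the Steering Committee: "The committee is comprised of at least two coordinating investigators". On the sponsor's seat it says: "A named member of the Sponsor's Clinical Affairs department will be part of the SC as a non-voting member".

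**Who may know CT results.** Protocol 7.11 allows unblinding of an asymptomatic subject whose first CT shows reduced mobility and whose valve gradients have increased. On who decides: "This determination will be made by the Core Lab and/or Coordinating Investigators". The decision is then "revealed to the study site through the LivaNova Project Manager or designee".

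**When results may be analysed.** SAP 4.1 places the main analysis after the first CT scans. SAP 4.2 mentions a hard lock only for the final analysis after the 1 year visits. SAP 4.3 adds that "internal evaluation could be requested during the study after assessing a reasonable number of subjects with results on the first CT scan", with every 50 subjects as the example.

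**What is masked.** The Protocol synopsis and SAP 2.2 blind the Core Lab to subject status, and blind asymptomatic subjects and their investigators to the CT findings.

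**What is programmed.** SAP 18.13 assigns the symptom group directly from the e-CRF field SCSYMPYN and names no adjudicated variable.

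**The concern.** The plan prevents symptom status from influencing the CT reading by blinding the Core Lab. It does not close the reverse path, in which knowledge of the CT reading influences the final symptom status. The people who confirm the symptomatic list may know some of the results, and the symptom definition leaves room for judgement.

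Symptom status defines the groups in secondary endpoint 1 (SAP 11.2) and in a subgroup analysis of the primary endpoint (Protocol 10.6, SAP 14). It is also a covariate in the logistic models (SAP 11.4) and the Cox models (SAP 11.5). If group membership is settled with knowledge of the outcome, the comparison of symptomatic with asymptomatic incidence partly reflects the review. Few positive subjects are expected, so one or two changes can move the comparison a long way.

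**Working it through.** **1. The plan's own figure.** Protocol 10.2 and SAP 2.3 give 75 evaluable scans, with an exact two-sided 90% CI narrower than 13% when the proportion is below 10%. The largest count below 10% of 75 is 7 (7/75 = 9.3%; 8/75 = 10.7%). The Clopper-Pearson 90% limits for 7/75 are 4.46% and 16.82%, a width of about 12.35 points. Enrolment is 75/0.85 = 88.2, or approximately 88. Both figures reproduce and neither is in dispute. Moving subjects between symptom groups leaves 7/75 and its interval unchanged.

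**2. Whether reviewers can know results.**
- Protocol 13.1 makes coordinating investigators the members of the Steering Committee, which confirms the list. Protocol 7.11 lets coordinating investigators decide on unblinding. Together these show possible knowledge of CT-positive, asymptomatic subjects with rising gradients.
- Those subjects are not on the symptomatic list at that point. This route matters only if the review can add names.
- Removing names with knowledge of the result would need another source. The main analysis and the internal evaluations (SAP 4.1 and 4.3) are possible sources, because review before data lock is not stated to mean review before first-CT results are analysed.
- No blinding statement in either document covers the symptom review.

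**3. Sensitivity of the split.** The documents give no expected number of positive or symptomatic subjects. The counts below are assumptions: 7 positives in 75, with 10 symptomatic subjects. Ratio = symptomatic incidence / asymptomatic incidence.

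| Change to the list | Symptomatic | Asymptomatic | Ratio |
|---|---|---|---|
| None | 2/10 = 20.0% | 5/65 = 7.7% | 2.6 |
| Strike one positive | 1/9 = 11.1% | 6/66 = 9.1% | 1.2 |
| Add two positives | 4/12 = 33.3% | 3/63 = 4.8% | 7.0 |

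**4. Starting from almost no association.** Assume 7 positives in 75 and 11 symptomatic subjects. The odds ratio is (positive symptomatic × negative asymptomatic) / (negative symptomatic × positive asymptomatic).
- No change: 1/11 against 6/64; (1×58)/(10×6) = 0.97.
- Add one positive: 2/12 against 5/63; (2×58)/(10×5) = 2.32.
- Add two positives: 3/13 against 4/62; (3×58)/(10×4) = 4.35.
- Strike the one positive: 0/10 against 7/65 (10.8%).
- Strike three CT-normal subjects: 1/8 against 6/67; (1×61)/(7×6) = 1.45.

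**5. Range over the assumed number of symptomatic subjects.** Adding one positive takes the odds ratio from 1.45 to 3.49 with 8 symptomatic at the start, and from 0.64 to 1.54 with 15.

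**6. Which status is analysed.** SAP 11.2 describes a validated list, while SAP 18.13 programs the raw field. The SAP does not say how a change made at review would reach the analysis, or whether it would.

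**The case against.** The other side has several sound points.

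- **Access is partial.** A reader might infer that the coordinating investigators receive everyone's first-CT results. Protocol 7.11 does not say so. The Core Lab may decide alone, and the rule covers only asymptomatic subjects with reduced mobility and increased gradients. The project manager relays a determination, and nothing describes CT listings going to the study team. The study team's access is an inference.
- **The power to change status is not stated.** The review could be ordinary data cleaning before lock. Status is the treating physician's, recorded at the CT visit. Protocol 11.1 gives the investigator responsibility for queries and keeps an audit trail, and Protocol 15.6 bars sponsor personnel from entering data in the sites' systems. With SCSYMPYN as the programmed variable, a committee decision might never reach the analysis.
- **The direction is unknown.** Only the list of symptomatic subjects is reviewed, which suggests names are more likely to be struck than added. Showing only an increase in the ratio would mislead.
- **Sampling error is large.** The exact 90% interval for 2/10 is 3.7% to 50.7%. The study is descriptive and makes no confirmatory test.

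These points narrow the concern but do not remove it. None supplies masking for the review. If validation can alter the status analysed, the route is open; if it cannot, SAP 11.2 should say so. A wide interval describes sampling error and does not correct for groups formed with knowledge of the outcome.

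**Conclusion.** The concern holds as an avoidable opportunity for bias, confined to the analyses that use symptom status. Secondary endpoint 1 and the symptom subgroup of the primary endpoint rest on largely the same split, so they are close to one exposure rather than two.

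In the ten-symptomatic illustration, one or two changes move the ratio from 2.6 to as low as 1.2 or as high as 7.0. These values rest on assumed counts and show sensitivity; they do not predict the size of any bias. The conclusion also assumes that some reviewers know some results and that a change made at review can enter the analysis. The documents allow both and establish neither.

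Two stronger readings are not supported. One is that bias has occurred: the documents show only that it could. The other is that the main result is compromised: the overall incidence and its interval do not depend on symptom status. The point is worth acting on because the correction is cheap.

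**What to change.** 1. In SAP 11.2, state that the symptom review uses a listing without CT, TEE or Core Lab results, and that the list is frozen before any analysis of first-CT results, including internal evaluations under SAP 4.3.
2. In SAP 11.2 and 18.13, state whether the validated status or raw SCSYMPYN is analysed. If it is the validated status, name the variable that holds it.
3. Report the number of changes from the e-CRF value, and give the split by unrevised e-CRF status as a sensitivity analysis.

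A rule that reviewers who know a subject's result must abstain is not advised. The committee needs only two coordinating investigators and the sponsor's member does not vote, so too few voters might remain. An abstention could also reveal the result, because the subjects referred for an unblinding decision are those with reduced motion.

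The cost is one masked listing, one extra table and a few sentences in the SAP. Sample size, data collection and staffing do not change.
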